3.2 Ethical Conduct of Study

The study shall be performed in accordance with Health Insurance Portability and Accountability Act (HIPAA) regulations, Food and Drug Administration (FDA) Good Clinical Practice (GCP) regulations as defined within the Code of Federal Regulations, 21 CFR parts 50, 56, and 312 and clinical safety data management (E2A) regulations. The Principal Investigator / Sponsor shall provide the IRB with all relevant material, including copies of the IND protocol, Informed Consent, Investigator's Brochure and any subject information or advertising materials. The study shall not be initiated until the IRB provides written approval of the protocol and the informed consent.

Each study subject shall be required to provide written authorization that their patient information can be disclosed and used by the Principal Investigator and other researchers as well as the Sponsor for the purposes of assessing the efficacy of the study drug and imaging protocol.

3.3 Patient Information and Informed Consent

In compliance with the requirements set forth by the FDA in 21 CFR Part 50, a properly written and executed Informed Consent shall be obtained from each study subject prior to enrollment and initial screening evaluations required by this protocol. The IC has been reviewed by the Sponsor for acceptability and shall be presented by the Principal Investigator, together with the IND protocol and

Investigatory New Drug
**Clinical Trial Protocol:
Choline C11 Injection**

Revision Date: _01/30/2015

Page 9 of 27

Investigator's Brochure, to the IRB for review and approval prior to the start of the study. The IC shall be written in such a way as to be fully comprehensible by the prospective study participant.

The Informed Consent shall be revised in the event new information becomes available during the study that may be relevant to the subject. Any revision shall be submitted to the IRB for review and approval before use.

It is the Principal Investigator's responsibility to obtain a properly written and executed Informed Consent from the study subject only after there has been an adequate explanation of the goals, methods, anticipated benefits and potential hazards of the study. The subject shall be given ample time to inquire about details of the study and decide whether to participate in the study. The IRB-approved IC shall be signed and dated by the subject and by the person conducting the informed consent discussion. A copy of the properly executed IC shall be provided to the study subject. The original signed informed consent shall be kept in a confidential location on site.

4. STUDY PATIENTS

4.1 Patient Study Population

Decatur Memorial Hospital (DMH), a not-for-profit division of Illinois Health & Science, will be the site designated for imaging the study subjects and evaluating the ^{11}C -choline PET/CT and PET/MR imaging data. Patients will be referred from within the institution as well as from outside treatment organizations. Urology, radiation oncology and medical oncology practices within an approximately 300 mile radius of the DMH imaging center will be contacted for enrollment of patients into this study. As such, this study will encompass patients being served in major cities, such as Chicago, St. Louis, Cincinnati, Louisville and Indianapolis who would otherwise have to seek ^{11}C -choline PET imaging at the Mayo Clinic in Rochester, MN. In the event that patients outside of the recruitment area wish to enroll in the clinical trial, they will also be considered. A primary source for patients will also be from The Cancer Care Institute, also a not-for-profit division of Illinois Health & Science. This phase III study is planned to provide expanded access to as many patients who elect to participate in the study that are over the age 18 and have experienced a biochemical relapse of prostate cancer after primary treatment.

4.1.1 Inclusion Criteria

Patients must meet all of the following criteria:

2. Suspected prostate cancer recurrence based upon elevated blood prostate specific antigen (PSA) levels following initial therapy.

Investigatory New Drug
**Clinical Trial Protocol:
Choline C11 Injection**

Revision Date: _01/30/2015

Page 10 of 27

3. Non-informative bone scintigraphy, computerized tomography (CT) or magnetic resonance imaging.

4.1.2 Exclusion Criteria

None.

4.2 Subject Withdrawal And Replacement

4.2.1 Criteria For Subject Withdrawal

Subject participation may be withdrawn / discontinued for the following reasons (but not limited to):

4. Patient request for any reason to discontinue participation within the clinical trial.
5. Patient non-compliance with the accepted protocol.
6. Suspension or discontinuation of the clinical trial by the Sponsor, Zevacor Molecular.

4.2.2 Procedures for Subject Withdrawal

Study patients who decide to discontinue the protocol and withdraw from the clinical trial will be seen and assessed by an Investigator. The reason(s) for the withdrawal and the date of the withdrawal will be documented in the study records for the patient.

If death is the reason for the withdrawal from the clinical trial, there are two options for categorizing as such: 1) progressive disease, or 2) a Serious Adverse Event (SAE). Although more than one SAE may be documented as reason for withdrawal, only one SAE will be documented as the cause of death.

At withdrawal, all on-going study-related AEs and SAEs must be followed until resolution, unless in the Investigator's opinion the condition is unlikely to be resolved due to the patient's underlying disease.

5. INVESTIGATIONAL PLAN

5.2 Expanded Access Study Protocol: Emergent Use

The study will consist of patients who have a biochemical relapse or other evidence of relapse after primary treatment. This study group of patients who, upon suspected recurrence, have subsequently experienced non-informative bone scintigraphy, computerized tomography (CR) or magnetic resonance imaging.

7. Informed consent will be obtained from all participants before any study related procedures are conducted. Each participant will be informed about the nature of the study, its purpose, and possible risks. Informed consent will be documented by using the written informed consent document approved by the local IRB at the Decatur Memorial Hospital.
8. At the time of referral, patients will be asked to bring their prior records as it pertains to their prostate cancer history. Data collected from outside records, such as radiographic studies, previous imaging studies and biopsies will be incorporated into the study record. Current data will be collected to support eligibility only; no historical data or future data will be collected.
9. Abstracted data for the study record will include:
 - a. Pathology reports
 - b. Imaging reports
 - c. Date(s) of biochemical relapse and coordinating PSA resultsOnce all records have been assessed for eligibility, an order for the ^{11}C -choline PET CT scan and MRI scan will be requested from the referring physician and patient will be scheduled and given the appropriate prep instructions.
10. Patients entered into the study will undergo a ^{11}C -choline PET CT scan and/or MRI scan. The CT scan will be performed with intravenous contrast unless deemed unsafe by lab values. The CT and MRI images will be evaluated for evidence of metastatic prostate cancer. The ^{11}C -choline PET CT and MRI images will be evaluated for evidence of metastatic prostate cancer.
11. Upon conclusion of each imaging protocol, the referring physician will receive written documentation of the results. At this time, the patient will be considered off study and no further follow up is required.

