4.1.1 Inclusion Criteria

Patients must meet all of the following criteria:

1. For biochemical relapse after primary treatment
 - a. PSA ≥ 0.2 ng/ml after radical prostatectomy confirmed at that level or higher on a subsequent test 3 months later
 - b. PSA increase ≥ 2 ng/ml from nadir following radiation therapy
 - c. PSA increase ≥ 2 ng/ml from nadir following radiation therapy plus androgen deprivation therapy with nadir defined with normalized testosterone level
 - d. Two consecutive PSA increases from nadir level after androgen blockade or androgen suppression therapy
2. Kidney function with GFR ≥ 60 mL/sec/1.73m² and Creatinine < 1.7 mg, collected within 90 days of planned scan
 - a. if GFR is $>$ or equal to 60 mL/sec/1.73m², PET/CT will be completed with contrast
 - b. if GFR is < 60 mL/sec/1.73m², PET/CT will be completed without contrast
 - c. if Creatinine is $>$ than 1.7 mg, Radiology will follow ACR recommendations as outlined in department policy
3. No known allergy to iodinated radiologic contrast media
4. Able to have MRI based on screening evaluation

Investigatory New Drug
**Clinical Trial Protocol:
Choline C11 Injection**

Revision Date: _01/30/2015

Page 13 of 59

if patient is found to be MRI incompatible, the ¹¹C-choline PET/MRI portion of the study will not be completed. These patients will not be included in the comparison data, but will have access to ¹¹C-choline PET/CT scan.

5. ECOG Performance Status of 0, 1, or 2

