5.2 Imaging Protocols - ^{11}C Choline PET/CT/MRI

1. ^{11}C choline PET/CT Imaging Protocol:
 - Patient should hydrate with 16 ounces of water prior to the imaging study
 - Fasting is required for at least 6 hours
 - Void prior to study
 - 15 - 20 mCi ^{11}C -choline IV Injection
 - 5 min delay after injection.
 - PET images skull base to mid thigh with 3 min per bed position
 - Image acquisition order changed due to bladder filling
 - If CT before MRI, then images obtained top to bottom
 - If MRI before CT, then images obtained bottom to top
 - CT skull base to mid thigh for attenuation correction
 - Use of IV contrast, if applicable, based on ACR IV contrast guidelines renal function screening protocol
 - Slice thickness 2.5, kvp 120, mA 100, exposure time 500, 80 - 100 cc contrast
 - Fusion of PET and CT images

2. MRI whole body imaging protocol:
 - No IV contrast
 - High resolution axial T2 prostate bed, axial DWI pelvis, coronal T2 skull base to mid thighs
 - Fusion of coronal and PET images

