7.4 Patient Safety Evaluations

Patient safety will be evaluated prior to participation in the study and before execution of each of the imaging protocols by screening process.

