2. STUDY OBJECTIVES

Based on these rationales, this protocol within this clinical trial will address the following objective:

- F. Provide expanded access to the drug ^{11}C -choline.

Investigatory New Drug
**Clinical Trial Protocol:
Choline C11 Injection**

Revision Date: _01/30/2015

Page 8 of 27

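### Expanded-access protocol: the CT contrast rule allows only a laboratory exception, and the main protocol's contrast-allergy criterion was not carried over

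*Combined protocol and SAP*

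**What the plan says.** The combined document holds a main protocol and a separate expanded-access protocol.

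**Expanded-access protocol.** Section 5.2 (Expanded Access Study Protocol: Emergent Use), item 10, sets the contrast rule: "The CT scan will be performed with intravenous contrast unless deemed unsafe by lab values". The PET/CT imaging protocol adds: "Use of IV contrast, if applicable, based on ACR IV contrast guidelines renal function screening protocol". Section 7.4 provides a general check: "Patient safety will be evaluated prior to participation in the study and before execution of each of the imaging protocols by screening process". Section 4.1.1 has two inclusion criteria: "Suspected prostate cancer recurrence based upon elevated blood prostate specific antigen (PSA) levels following initial therapy" and "Non-informative bone scintigraphy, computerized tomography (CT) or magnetic resonance imaging". Section 4.1.2 lists no exclusions. The only objective in Section 2 is access: "Provide expanded access to the drug" ¹¹C-choline.

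**Main protocol.** Section 5.1 item 5, the PET/CT imaging protocol and Section 7.4 carry the same contrast and screening sentences. Section 4.1.1 adds criterion 3: "No known allergy to iodinated radiologic contrast media". Item 2b of that section gives a route for men with low GFR: "PET/CT will be completed without contrast". Section 5.1 item 4 also lists allergies among the data abstracted to the study record.

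**The concern.** The contrast rule makes contrast the default and recognises one kind of exception, a laboratory one. A known allergy is a matter of history, and renal laboratory results do not reveal it. In the main protocol this does little harm, because criterion 3 has already removed men with known allergy before the rule is applied. The expanded-access protocol keeps the rule and drops that precondition.

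The man at risk is one with known allergy to iodinated contrast and acceptable renal results. The main protocol would refuse him and expanded access admits him. Admitting him suits the purpose of expanded access. The difficulty is that the instruction he then meets points towards iodinated contrast, and no specific condition points away from it. What is at stake is an avoidable exposure that the sponsor foresaw when writing the main protocol.

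**Working it through.** No calculation applies: the point depends on no sample size, error rate or effect, and there is no figure in the plan to reproduce. The check is a comparison of every text that bears on whether contrast is given.

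| Text | Main protocol | Expanded access | Names contrast allergy? |
|---|---|---|---|
| Contrast unless laboratory values make it unsafe | 5.1, item 5 | 5.2, item 10, same sentence | No |
| Contrast line in the PET/CT imaging protocol | 5.2 | 5.2 (Imaging Protocols), same line | No; the basis is renal function |
| Safety screening before each imaging protocol | 7.4 | 7.4, same sentence | No; no items are listed |
| No known allergy to iodinated contrast | 4.1.1, criterion 3 | Absent | Yes, main protocol only |
| Allergies abstracted to the record | 5.1, item 4 | Absent from 5.2, item 9 | Allergies in general, main protocol only |

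1. The three general texts are the same in both protocols (3 of 3).
2. The explicit contrast-allergy statement appears once in the main protocol and nowhere in the supplied expanded-access text.
3. Now follow a man with known allergy and acceptable renal results through expanded access. He can meet both inclusion criteria, and there are no exclusions to stop him. Under item 10 his laboratory values do not block contrast, and renal screening does not block it either. He is left to the Section 7.4 screen, which does not say that allergy is asked about or what follows if it is reported.
4. The data rules do not fill the gap. Item 8 limits collection to what supports eligibility. Item 9 abstracts pathology reports, imaging reports, and relapse dates with PSA. Allergy is not an eligibility item, so nothing there calls for it to be recorded.
5. Section 8.2 keeps resuscitation equipment and staff at hand. That deals with a reaction after it starts and does not prevent exposure.

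**The case against.** The strongest reply is that item 10 should not be read alone. Section 7.4 requires a safety evaluation before each imaging protocol, which is the right moment to ask about allergy. The imaging line makes contrast conditional. A referring physician must order the scan, and Section 8.2 anticipates anaphylaxis. Read together, these leave the clinician free to withhold contrast. The radiology department's policy and the screening forms are not in the supplied text, and consent pages were removed, so allergy may well be asked about in practice.

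Much of this stands. It lowers the risk and rules out any claim that allergic men will in fact receive contrast. It does not close the gap, for two reasons. The conditional imaging line names renal function as its basis, and the screening sentence names nothing. The main protocol has both of those sentences word for word, yet still states the allergy condition separately. The main protocol's reference to department policy (Section 4.1.1, item 2c) concerns creatinine and was not carried into expanded access.

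Two further objections concern the remedy. If only item 10 and Section 7.4 change, the imaging line will still mention only renal screening, and item 9 will still not record allergies. That is fair, and both can be tidied in the same amendment. It is also said that sending every man with a reported allergy to non-contrast CT removes clinical discretion. It does, but it is milder than the main protocol, which bars such men altogether.

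**Conclusion.** The concern holds. Followed as written, the expanded-access contrast rule directs a man with known iodinated-contrast allergy and acceptable renal results towards contrast, and no specific text directs otherwise. This should be corrected as a patient-safety gap in one instruction, partly covered by general screening.

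Its size in patients is unknown. The documents give no contrast-allergy rate, item 10 allows MRI without CT, and the general screen may catch cases. Confidence is high in the comparison of texts; how often harm would follow is not claimed. The conclusion covers the supplied text only and does not assess the consent pages or outside policies.

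No statistical result depends on it. Sections 5.5 and 5.6 of the expanded-access protocol say that its data are not analysed beyond clinical diagnosis and are not published.

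**What to change.** Amend the expanded-access protocol in two places:

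1. **Section 5.2, item 10:** make known allergy to iodinated contrast a second reason to withhold contrast, alongside unsafe laboratory values.
2. **Section 7.4:** state that the pre-imaging screen asks about known allergy to iodinated contrast, as a condition on contrast and not on access. A man who reports it has PET/CT without contrast.

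The non-contrast route follows by analogy from the main protocol's provision for GFR below 60 (Section 4.1.1, item 2b). The main protocol has no such route for allergy, because criterion 3 makes these men ineligible. Copying criterion 3 across would also close the gap, but it would shut out men whom expanded access is meant to reach.

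Optional in the same amendment: add allergy to the contrast line of the imaging protocol, and list allergies among the data abstracted under item 9, so that the sections agree and the answer is recorded.

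The core change costs one phrase and one screening question. The downside is that men with known allergy get a CT without contrast. Nobody loses access.

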5.2 Imaging Protocols - ^{11}C Choline PET/CT/MRI

3. ^{11}C choline PET/CT Imaging Protocol:
 - Patient should hydrate with 16 ounces of water prior to the imaging study
 - Fasting is required for at least 6 hours
 - Void prior to study
 - 15 - 20 mCi ^{11}C -choline IV Injection
 - 5 min delay after injection.
 - PET images skull base to mid thigh with 3 min per bed position
 - Image acquisition order changed due to bladder filling
 - If CT before MRI, then images obtained top to bottom
 - If MRI before CT, then images obtained bottom to top

Investigatory New Drug
**Clinical Trial Protocol:
Choline C11 Injection**

Revision Date: _01/30/2015

Page 12 of 27

- CT skull base to mid thigh for attenuation correction
 - Use of IV contrast, if applicable, based on ACR IV contrast guidelines renal function screening protocol
 - Slice thickness 2.5, kvp 120, mA 100, exposure time 500, 80 - 100 cc contrast
 - Fusion of PET and CT images
4. MRI whole body imaging protocol:
- No IV contrast
 - High resolution axial T2 prostate bed, axial DWI pelvis, coronal T2 skull base to mid thighs
 - Fusion of coronal and PET images

5.3 Imaging Technology

The imaging studies referenced above will be conducted as defined in Section 5.2 above. The CT and MR studies must be performed as one continuous procedure using the GE Trimodality PET Imaging System. This will require the patient to be immobile for approximately 60 minutes as each imaging study is executed.

The GE Trimodality PET Imaging System consists of the following integrated equipment: GE Discovery PET/CT 7.0 Imaging System, a GE Discovery MR750w 3.0T Imaging System, and the Lateral Docking Trimodality Patient Transporter. This system will allow for the combined imaging of PET, CT, and MR modalities in one integrated session using the Lateral Docking Transporter to ensure image synchronization between the modalities.

5.4 Imaging Review and Interpretations

5.4.1 Image Review

For this Expanded Access protocol, there will not be any study related interpretation or use of any imaging.

5.4.3 Image Assessment Criteria

NONE

5.5 Study Data – Statistical Analysis

- Sample Size:

Investigatory New Drug
**Clinical Trial Protocol:
Choline C11 Injection**

Revision Date: _01/30/2015

Page 13 of 27

This study has been established to provide expanded access to the radioactive diagnostic imaging agent Choline C11 Injection in conjunction with PET/CT and/or MRI scans.

It is anticipated that during this study at least 100 patients maybe admitted into the study under expanded access. In the event that more than 100 patients request to be permitted into the expanded access study, Zevacor Molecular, the study sponsor, will formally petition the FDA to increase the study population.

- **Data Analysis:**

This protocol is to provide expanded access only. The patient data obtained for this protocol will not be further analyzed beyond that need for clinical diagnosis.

5.6 Publishing the Study Data

Study data for this expanded access protocol will not be published.

6.0 CONTRAINDICATIONS, WARNINGS AND PRECAUTIONS

6.1 Contraindications

None

6.2 Warnings and Precautions

- Imaging errors have been reported during previous clinical studies with ¹¹C-choline PET and PET/CT imaging. A negative image does not rule out the presence of recurrent prostate cancer and a positive image does not confirm the presence of recurrent cancer. ¹¹C-choline uptake is not specific for prostate cancer and may occur with other types of cancer, such as lung carcinoma and brain tumors.
- Blood PSA levels < 2 ng/mL have been associated with poor performance ¹¹C-choline PET imaging, with indications of higher numbers of false positive and false negative results.
- Tissue inflammation as well as prostatic hyperplasia have been associated with false positive ¹¹C-choline PET images.

Investigatory New Drug
**Clinical Trial Protocol:
Choline C11 Injection**

Revision Date: _01/30/2015

Page 14 of 27

- Concomitant colchicine or androgen-deprivation therapeutic drugs, such as luteinizing hormone-releasing analogs and anti-androgen drugs, may interfere with ^{11}C -choline PET imaging. One published report of ^{18}F methylcholine PET imaging indicated that discontinuation of colchicine for two weeks resolved the colchicine effect. The impact of discontinuation of androgen-deprivations therapy upon ^{11}C -choline PET imaging has not been established.

6.3 Limitation of Use

^{11}C -choline PET imaging is NOT a replacement for histologic verification of relapsed prostate cancer.

7. ASSESSMENT OF SAFETY

7.1 Radiation Safety – Drug Handling

^{11}C -choline is a radioactive drug and will be handled with appropriate safety measures to minimize radiation exposure during administration. The use of waterproof gloves and effective shielding when handling ^{11}C -choline will be required. Radiopharmaceuticals, such as ^{11}C -choline will only be used by or under the control of physicians who are qualified by specific training and experience in the safe use and handling of radioactive materials, and whose experience and training have been approved by the appropriate governmental agency authorized to license the use of radionuclides.

^{11}C -choline will be delivered to a Certified Nuclear Medicine Technician (CNMT) or equivalently qualified personnel in individual, single dose syringes contained within a NRC/DOT approved syringe shield specifically designed for minimizing radiation exposure during handling. The safe handling of Radioactive Material will be as defined within the Sponsors' radioactive material license issued by the Illinois Energy Management Agency (IEMA), the state nuclear regulatory agency responsible for radioactive material within the State of Illinois.

